1. BACKGROUND

CB-03-01 (cortexolone 17 α -propionate) is a steroidal antiandrogen that is being developed as a 1% cream for the topical treatment of acne vulgaris, an androgen-dependent skin disorder. CB-03-01 binds to the human androgen receptor displacing the androgenic hormones and acts as an androgen antagonist. In human plasma, CB-03-01 is rapidly metabolized to parent cortexolone so that its systemic bioavailability after topical application is anticipated to be low. Cortexolone, the main by-product, is a physiological component of the pool of endogenous corticosteroids, and is an intermediate in the synthesis of glucocorticoids, but it only exhibits weak glucocorticoid properties [1].

CB-03-01 could offer advantages over existing products for acne vulgaris due to its potential efficacy and lack of systemic antiandrogen activity. Because its pharmacological action appears to be limited to the local site of application, use of CB-03-01 may be able to mitigate the side effects related to systemic exposure to hormonal agents currently used in the treatment of acne.

2. RATIONALE

To date, CB-03-01 cream has been used for treatment of acne vulgaris for up to 12 weeks with no material safety issues to note. Given that acne vulgaris is a chronic condition which typically waxes and wanes over time and often requires extended (and sometimes intermittent) treatment, this study is designed to investigate the long-term safety of CB-03-01 cream, 1%.

3. OBJECTIVE

The primary objective of this study is to determine the long-term safety of CB-03-01 cream, 1% applied twice daily for an additional nine months in subjects with acne vulgaris that participated in the Phase 3 pivotal studies for a total treatment of up to 12 months.

4. STUDY DESIGN

This is a multicenter, open label, long-term extension study for CB-03-01 cream, 1% focused on safety in male and female subjects, 9 years or older who completed one of the Phase 3 pivotal studies [CB-03-01/25 and CB-03-01/26]. Subjects will apply the active medication (CB-03-01 cream, 1%) twice daily to the entire face and, if designated by investigator AND desired by subject, truncal acne for nine additional months of treatment. Thus, overall subjects will be exposed to CB-03-01 cream, 1% for a total treatment of up to 12 months (0 or 3 months in the Phase 3 pivotal study and an additional nine months in this long-term safety study).

For this Long-Term Follow-Up (LTF) study, subjects must rollover from the Phase 3 pivotal study (CB-03-01/25 and CB-03-01/26) into this study AT or WITHIN THREE (3) DAYS of Visit 4-Pivotal.

Subjects will treat facial acne per protocol for nine months. Treatment of truncal acne will be discussed by the investigator and subject. If the subject desires, the truncal treatment area will be defined and agreed upon by the investigator and the subject. If the investigator and subject designate a treatment area for truncal acne, the subject must continue to treat this area for the duration of the study per protocol as detailed in [Section 6.2](#). If the investigator and subject do not designate a treatment area for truncal acne at Baseline [Visit 4-LTF], one may be designated at subsequent visits (e.g., if acne worsens in the truncal area), but once treatment begins in such treatment area, the subject must continue to treat this area per protocol for the remainder of the study.

Treatment on the face and/or trunk may be discontinued if/when acne clears (achieves an IGA of grade 0 or “minimal” grade 1) and re-instated if/when acne worsens (IGA \geq 2), according to the assessment of the investigator for each respective treatment area (i.e., face and trunk). Note: Subjects must be seen by the investigator via a routinely scheduled study visit or an unscheduled visit to change (i.e., restart or stop) test article dosing on either treatment area (i.e., face and trunk).

Subjects (approximately 600) will be rolled over from the Phase 3 pivotal studies [CB-03-01/25 and CB-03-01/26] into this long-term, safety study in order to achieve at least 300 subjects on-study at 6 months and 100 subjects on-study at 12 months. These treatment durations include the 0 or 3 months of active treatment in the Phase 3 pivotal studies (CB-03-01/25 and CB-03-01/26).

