Study Procedures	
The study will consist of a Baseline Visit, follow-up visits at LTF-Months 1, 3, 6, and 9, and follow-up phone calls at LTF-Months 4.5 and 7.5. For subjects in the Phase 3 pivotal studies randomized to active (CB-03-01 cream, 1% twice daily), the total treatment period will be 12 (3+9) months; whereas for those subjects in the Phase 3 pivotal studies randomized to vehicle, the total treatment period will be 9 (0+9) months.
 
For this Long-Term Follow-Up (LTF) study, subjects must rollover from the Phase 3 pivotal study (CB-03-01/25 and CB-03-01/26) into this study AT or WITHIN THREE (3) DAYS of Visit 4-Pivotal.
 
During the LTF study, subjects will treat facial acne per protocol for nine months. Treatment of truncal acne is optional and will be discussed by the investigator and subject (see Section 10.3). If truncal acne is to be treated, the subject must continue to treat the designated treatment area for the remainder of the study as detailed in Section 6.2. Treatment on face and/or trunk for a subject may be discontinued if/when acne is under successful control (achieves an IGA of grade 0 or “minimal” grade 1) and re-instated if/when acne worsens (IGA ≥ 2) according to the assessment of the investigator for each respective treatment area. Subjects must be seen by the investigator via a scheduled or unscheduled visit to change (i.e., restart or stop) test article dosing. Acne will be managed per protocol as detailed in Section 6.2 and Section 8.2.
 
Visit 4-LTF (Baseline): At Visit 4-LTF, study staff will explain the study procedures and an informed consent/assent must be signed prior to the initiation of any study-related procedures. At this visit, inclusion/exclusion criteria will be reviewed to determine subject eligibility. Demographics and medical/dermatological history data will be used from the Phase 3 pivotal study. A brief physical examination including vital signs and a UPT (if applicable) will be performed. Note: If Visit 4-Pivotal and Visit 4-LTF occur on the same day, the results of the UPT performed during the End of Study (EOS) visit of the Phase 3 pivotal study can be used as Baseline data. IGA for the face and local skin reactions (LSRs) [pre-application for the face] performed during the EOS Visit of the Phase 3 pivotal study (Visit 4-Pivotal) will be used as Baseline data. Treatment of truncal acne will be discussed by the investigator and subject. If the subject desires, the truncal treatment area will be defined and agreed upon by the investigator and the subject, with the percent body surface area (BSA) to be treated recorded. If the investigator

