⁹ LSRs assessed at the EOS Visit of the Phase 3 pivotal trial (Visit 4-Pivotal) will be used as pre-application data for face. LSRs [pre-application] will be assessed for trunk at Visit 4-LTF. After ITA application in the clinic, LSRs will be assessed post-application (Visit 4-LTF) for face and trunk, as applicable.

¹⁰ Any ongoing concomitant medications and procedures will be reviewed at Visit 4-LTF.

¹¹ Instruct subject (and parent/guardian, if applicable) on ITA application and provide instruction sheet. Review compliance with respect to the amount and number of doses applied since the last visit.

¹² Dispense subject diary, as needed.

ABBREVIATIONS

AE	Adverse Event
BID	Twice a day
BSA	Body Surface Area
CB-03-01	Cortexolone 17 α -propionate
CLIA	Clinical Laboratory Improvement Amendments
CFR	Code of Federal Regulations
CRF	Case Report Form
CRO	Contract Research Organization
CV%	Percent Coefficient of Variation
EDC	Electronic Data Capture
EOS	End of Study
FDA	Food and Drug Administration
GCP	Good Clinical Practices
IGA	Investigator's Global Assessment
IND	Investigational New Drug
IRB	Institutional Review Board
ITA	Investigational Test Article
ITT	Intent-to-Treat
IUD	Intrauterine Device
LSR	Local Skin Reaction
LTF	Long-Term Follow-Up
MedDRA	Medical Dictionary for Regulatory Activities
OTC	Over-the-Counter
PP	Per-Protocol
QA	Quality Assurance
RX	Prescription
SAE	Serious Adverse Event
TEAE	Treatment Emergent Adverse Event
●	●
UPT	Urine Pregnancy Test
WOCBP	Women of Childbearing Potential

TABLE OF CONTENTS

Protocol Approval.....	2
Study Acknowledgement.....	3
Protocol Synopsis.....	4
Schedule of Events.....	11
Abbreviations.....	13
Table of Contents.....	14
1. Background.....	16
2. Rationale.....	16
3. Objective.....	16
4. Study Design.....	16
5. Study Population.....	17
5.1 Subject Eligibility.....	17
5.1.1 Inclusion Criteria.....	17
5.1.2 Exclusion Criteria.....	18
5.1.3 Subject Withdrawal Criteria.....	19
6. Test Articles and Regimen.....	19
6.1 Description.....	19
6.2 Instructions for Use and Application.....	19
6.3 Warnings, Precautions and Contraindications.....	21
7. Randomization Assignment.....	21
8. Prior and Concomitant Therapies.....	21
8.1 Prohibited Medications or Therapies.....	22
8.2 Allowed Medications or Therapies.....	22
9. Study Procedures.....	23
9.1 Visit 4-LTF Baseline (LTF-Day 1) [Visit 4-Pivotal + 3 days].....	23

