6.2 Instructions for Use and Application

Subjects will treat facial acne per protocol for nine months. Treatment of truncal acne will be discussed by the investigator and subject. If the subject desires, the truncal treatment area will be defined and agreed upon by the investigator and the subject. If the investigator and subject designate a treatment area for truncal acne, the subject must continue to treat this area per protocol for the duration of the study as detailed below. If the investigator and subject do not designate a treatment area for truncal acne at Baseline (Visit 4-LTF), one may be designated at subsequent visits (e.g., if acne worsens in the truncal area), but once treatment begins in such treatment area, the subject must continue to treat this area per protocol for the remainder of the study.

At the first visit, the subjects will be instructed to wash the area to be treated (entire face and trunk, if applicable) with mild soap and water and then dry the area gently. The study staff will then instruct the subject and parent/guardian (if applicable) on how to dispense the test article, how much of the test article to use, and where to apply the assigned test article. The first application of the test article should be applied in the office at Visit 4-LTF under supervision of the study staff after the treatment areas have been determined, except for those subjects with clear facial acne and no truncal acne. For subjects starting treatment at subsequent visits, the first dose of the test article will be applied at that visit under supervision of the study staff. Typically, for the face, about one (1) gram of the test article will be dispensed onto a fingertip and applied by gently dabbing small amounts of the test article on multiple regions of the face (e.g., forehead, nose, cheeks, chin). Using a fingertip, the test article will be spread to provide a thin, uniform layer of the test article **over the entire face**. In addition, if applicable, subjects who choose (with investigator's approval) to treat truncal acne should apply a thin uniform application of the test article to the

designated area(s) of the trunk (e.g., the shoulders, chest, and/or back). *Note: one (1) gram of cream will cover approximately a 8.5" x 11" (~22 cm x 28 cm) area.*

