9. STUDY PROCEDURES

The study will consist of a Baseline Visit, follow-up visits at Months 1, 3, 6, and 9, and follow-up phone calls at Months 4.5 and 7.5. For subjects in the Phase 3 pivotal studies randomized to active (CB-03-01 cream, 1% twice daily), the total treatment period will be 12 (3+9) months; whereas for those subjects in the Phase 3 pivotal studies randomized to vehicle, the total treatment period will be 9 (0+9) months.

During the LTF study, treatment on face and/or trunk for a subject may be discontinued if/when acne is under successful control (achieves an IGA of grade 0 or "minimal" grade 1) and re-instated if/when acne worsens ($IGA \geq 2$), according to the assessment of the investigator for each respective treatment area. Subjects MUST be seen by the investigator via a scheduled or unscheduled visit to change (i.e., restart or stop) test article dosing).

Specific activities for each study visit are listed below.

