### 7.9.1 *Local Skin Reactions (LSRs)*

LSRs (telangiectasia, skin atrophy, striae rubrae, erythema, edema, scaling/dryness, stinging/burning, and pruritus) will be listed separately for face and trunk ([Listing 16.2.9.1](#), [Listing 16.2.9.2](#)) and summarized separately for face and trunk by the frequency of each individual LSR and severity at each visit ([Table 14.3.5.1](#), [Table 14.3.5.2](#)).

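### Trunk results are tabulated only by LTF visit although trunk treatment can start late, so the LTF Month 9 trunk column can mix about 3 to 9 months since trunk start

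*Protocol*

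**What the plan says.** **Total exposure.** Protocol section 4 covers face and optional trunk together and then states: "Thus, overall subjects will be exposed to CB-03-01 cream, 1% for a total treatment of up to 12 months". It gives the components as "0 or 3 months in the Phase 3 pivotal study and an additional nine months in this long-term safety study". The overall-exposure row in the Schedule of Events (9 or 12 months at Visit 10) is not split by treatment area.

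**Start of trunk treatment.** A truncal area can be chosen at Visit 4-LTF. If it is not, Protocol 6.2 allows that "one may be designated at subsequent visits (e.g., if acne worsens in the truncal area". Protocol 9.2 and 9.5 repeat this for scheduled and unscheduled visits.

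**Baseline.** For the face, the Synopsis (Study Procedures) uses "IGA for the face and local skin reactions (LSRs) [pre-application for the face] performed during the EOS Visit of the Phase 3 pivotal study". For the trunk, footnote 9 of the Schedule of Events says "LSRs [pre-application] will be assessed for trunk at Visit 4-LTF". The Synopsis (Study Measurements) adds that, when trunk treatment begins after Visit 4-LTF, Baseline is the visit of first application.

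**Tables.** Under SAP 7.9.1, LSRs are "summarized separately for face and trunk by the frequency of each individual LSR and severity at each visit". Protocol 17.3.2 summarises IGA for each area at Baseline and LTF Months 1, 3, 6 and 9. No trunk table by time since trunk start is described.

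**The concern.** Long-term safety is the primary objective. Protocol 10.2 singles out telangiectasia, skin atrophy and striae rubrae as reactions associated with topical steroids and has them scored separately on face and trunk. If such reactions accumulate with time at the site, the useful trunk question is how often they occur after a given time on trunk treatment. A table indexed by LTF visit answers that only if everyone starts the trunk at Visit 4-LTF, and the protocol does not require that.

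Two things could go wrong. Recent starters could dilute the trunk frequencies in the later columns. A subject's last score before any truncal application could also appear in a column read as on-treatment. In addition, the 12-month figure carries no note that it does not describe the trunk.

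**Working it through.** **1. The plan's own total.** Protocol section 9 says for subjects on active in the pivotal study that "the total treatment period will be 12 (3+9) months", and for those on vehicle that "the total treatment period will be 9 (0+9) months". The sums 3 + 9 = 12 and 0 + 9 = 9 reproduce both. The total is correct per subject.

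**2. Was the trunk treated in the pivotal studies?** The documents do not say so outright. The evidence against it is:
- Facial IGA and LSRs carry over from Visit 4-Pivotal, while trunk IGA and LSRs are first taken at Visit 4-LTF, before the first truncal application (Protocol 9.1).
- Percent BSA of the trunk is recorded when the area is defined in this study (Protocol 10.3).
- SAP 2.5 describes the rollover population as having facial acne.

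This is a strong inference. If it holds, the 3 pivotal months do not count towards the trunk.

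**3. Time since trunk start at Visit 10.** Inputs are the visit days and windows in the Schedule of Events: Visit 4-LTF Day 1, Visit 5 Day 29 ± 10, Visit 6 Day 85 ± 15, Visit 8 Day 183 ± 15, Visit 10 Day 274 ± 21.

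- Nominal days = 274 − start day
- Shortest = (274 − 21) − (start day + window)
- Longest = (274 + 21) − (start day − window)
- Months = days / 30.44

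| Trunk start | Nominal days | Months | Range with windows, days (months) |
|---|---|---|---|
| Visit 4-LTF | 274 − 1 = 273 | 9.0 | 252 to 294 (8.3 to 9.7) |
| Visit 5 | 274 − 29 = 245 | 8.0 | 214 to 276 (7.0 to 9.1) |
| Visit 6 | 274 − 85 = 189 | 6.2 | 153 to 225 (5.0 to 7.4) |
| Visit 8 | 274 − 183 = 91 | 3.0 | 55 to 127 (1.8 to 4.2) |

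All four rows fall in the same LTF Month 9 column. A start at an unscheduled visit after Visit 8 would be shorter still. The longest possible truncal time is 294 days, or 9.7 months.

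**4. Which trunk score is Baseline?**
- Synopsis (Study Measurements): Visit 4-LTF, or the visit of first application if later.
- Protocol 10.1 and SAP 3.1: Visit 4-LTF only.
- Protocol 17.3.2: labelled as the pivotal end-of-study visit, for face and trunk alike.

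Take a subject who starts the trunk at Visit 6. Truncal time at that visit is 85 − 85 = 0 days. Under the Synopsis the Visit 6 score is Baseline; by visit it is an LTF Month 3 result. Under SAP 3.1 the subject may have no trunk Baseline at all, because the trunk is assessed at Visit 4-LTF only if applicable and SAP 7.4 does not replace missing values.

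**5. Is truncal duration summarised elsewhere?** Protocol 17.3.1 plans applications and days dosed for each area. SAP 7.8.1 splits doses and compliance by area, and SAP 7.8.4 lists truncal application dates. SAP 7.8.2, the exposure summary, names no split by area, although SAP 1.1 declares no change from the protocol. No described summary counts subjects by duration of truncal treatment.

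**The case against.** A reader might infer that the design claims 12 months for both face and trunk. It does not. The sentence in Protocol section 4 is about subjects, says up to, and is arithmetically right; no passage claims 12 months on the trunk. A reader might also infer that the sample-size limit of 3% for 100 subjects at 12 months fails for the trunk. That limit concerns important AEs per subject, not treatment areas, so the lack of a truncal counterpart is not a defect.

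Further points on the other side are fair:
- The labels denote time in this study and stop at LTF Month 9, so they do not contradict a truncal maximum of about 9 months.
- The endpoint is defined at each collected time point, so the visit tables must stay.
- Treatment of an area can stop and restart (Protocol 6.2), so time since first truncal application is not time on treatment either.
- Worsening acne is only an example of why a truncal area might be added late; the documents do not support saying that late areas enter for that reason.
- The protocol already plans days dosed by area, and the table shells are not available to this review.

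These points limit the remedy to supplementary tables shown with days dosed. They leave the mixing of durations within a visit column, which does not depend on the inference about the pivotal studies. They also leave the unresolved trunk Baseline.

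**Conclusion.** The point stands as a weakness in how trunk results are indexed and in how trunk Baseline is defined. At nominal visit days, the LTF Month 9 trunk column can span 91 to 273 days since trunk start (3.0 to 9.0 months), and pre-treatment trunk scores of late starters can enter on-treatment columns. Both follow directly from the protocol's permission to start the trunk late.

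The statement that the 12-month total does not describe the trunk, and that truncal exposure is at most about 9 months (9.7 with the visit window), rests on the strong but unstated premise that the pivotal studies did not treat the trunk.

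A reader might conclude that the Month 9 trunk column understates local reactions after nine months' use. The documents do not establish that: it would need an appreciable number of late starters and reactions that increase with duration. The number of late starters is not given, so the size of any dilution is unknown.

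**What to change.** 1. In SAP 3.1, 7.6 and 7.9.1, take trunk Baseline as the visit where trunk treatment is first applied, as in the Synopsis, and keep pre-treatment trunk scores out of the on-treatment columns. Use the pivotal end-of-study label for the face only.
2. Keep the by-visit trunk tables. Add supplementary trunk LSR and IGA tables by time since first truncal application (0-3, >3-6 and >6-9 months), shown with truncal days dosed because treatment can pause. Fix the cut-offs in days: a baseline starter at nominal Visit 10 has 273 days, and 273 / 30.44 = 8.97 would narrowly miss a literal nine months. Let the last band run to the end of the Visit 10 window.
3. In SAP 7.8.2, summarise days dosed by area as Protocol 17.3.1 plans, and count subjects with at least 3, 6 and 9 months of truncal treatment. These counts would also show how many late starters there are.
4. State in SAP 2.4 that the 12-month figure does not describe truncal exposure.

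**Cost.** SAP wording and a few extra tables, some with small cells, plus a shorter truncal exposure statement. No new data are needed: the diary records the area treated, and SAP 7.8.4 already lists truncal application dates. Patient management is unaffected.

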5. STUDY POPULATION

5.1 Subject Eligibility

To be included in the study, subjects must meet the following inclusion and none of the exclusion criteria.

5.1.1 Inclusion Criteria

1. Subject must have been enrolled in one of the Phase 3 pivotal studies [CB-03-01/25 and CB-03-01/26], completed the assigned treatment regimen without any material non-compliance with study requirements or test article dosing (compliance \geq 80%), and completed the final study visit (Visit 4-Pivotal).
2. Subject agrees to treat his/her facial acne and truncal acne (if designated by investigator AND desired by subject) during the nine month study period per protocol. Note: Subjects who are clear (IGA=0) at Visit 4-Pivotal are also eligible for the study.

3. Females must be post-menopausal⁶, surgically sterile⁷, or using highly effective birth control methods.^{8,9} Women of childbearing potential (WOCBP)¹⁰ must have a negative urine pregnancy test (UPT) at Visit 4-LTF (or Visit4-Pivotal, if the visits occur on the same day).
4. Subject has provided written informed consent/assent. A subject under 18 years of age must provide written informed assent and be accompanied by the parent or legal guardian at the time of assent/consent signing. The parent or legal guardian must provide informed consent for the subject. If a subject becomes 18 years of age during the study, the subject must provide written informed consent at that time to continue study participation.
5. Subject is willing to comply with study instructions and return to the clinic for required visits.

5.1.2 Exclusion Criteria

1. Subject is pregnant, lactating, or is planning to become pregnant during the study.
2. Subject has any skin pathology or condition that could interfere with the safety evaluation of the test products or requires the use of interfering topical or systemic therapy (see [Section 8.1: Prohibited Medications and Therapies](#)).
3. Subject has any condition which, in the investigator's opinion, would make it unsafe or unsuitable for the subject to participate in this research study.
4. Subject plans to use any other investigational drug or device during participation in this study.
5. Subject, and parent/guardian if required, is unable to communicate or cooperate with the investigator due to language problems, poor mental development, or impaired cerebral function.
6. Subject may be unreliable for the study including subjects who engage in excessive alcohol intake or drug abuse, or subjects who are unable to return for scheduled follow-up visits.
7. Subject has known hypersensitivity or previous allergic reaction to any of the active or inactive components of the test article.
8. Subject is or plans to use any topical anti-acne preparations (excluding CB-03-01 cream) or procedures on the face (or trunk, if applicable) or any systemic anti-acne

⁶ Defined as amenorrhea greater than 12 consecutive months.

⁷ Hysterectomy, bilateral tubal ligation (at least six months prior to study entry), or bilateral oophorectomy.

⁸ Highly effective contraception includes a) total abstinence, b) oral, injected, or implanted hormonal methods of contraception for at least two complete cycles (i.e., eight to twelve weeks) prior to it being considered highly effective, c) intrauterine device (IUD) for at least one week prior to it being considered highly effective, d) partner vasectomy (performed at least six months prior to study entry), or e) double barrier methods of contraception [barrier methods include male or female condom, diaphragm with spermicidal foam/gel/film/vaginal suppository, cervical cap with spermicides, or contraceptive sponge].

⁹ WOCBP taking hormonal therapy for any reason must not change their dosing regimen during the study.

¹⁰ WOCBP include any female who has experienced menarche or is 10 years of age or older and who has not undergone successful surgical sterilization (hysterectomy, bilateral tubal ligation, or bilateral oophorectomy) or is not postmenopausal.

medications (as detailed in [Section 8.1](#): Prohibited Medications and Therapies) during the study

